### **3.3 Minorities and Women**

Both genders and from all racial/ethnic groups will be recruited equally into this trial.

## **Section 4.0 Registration Procedure:**

The date of enrollment is the date of consent. However, all eligibility criteria do not need to be met until the date of the first study related treatment.

All subjects need to sign the consent form in order to enroll on the study. They will receive a copy of the consent form. In case of any issues, the treating physician or PI should be called for clarification. The subject will be registered as described below in section 4.2.

#### **4.1 Recruitment**

Subjects, who are referred to the Nebraska Medical Center (NMC)/UNMC with a diagnosis of MM and considered eligible for autologous hematopoietic stem cell transplantation will be identified from the outpatient clinics or inpatient service. Potential subjects will be recruited for the study by the principal investigator (PI), co-investigators or participating clinicians.

Screening eligibility is based on standard clinical care performed by Bone Marrow Transplant (BMT) physician. Pre-transplant work up performed for determining the eligibility of the subject for high dose chemotherapy and autologous transplant, prior to signing of consent form will be acceptable. All other study related interventions and evaluation can only be performed after signing the consent form.

If the subject is screened as potentially eligible, he/she will then be offered the option to participate. An informed consent will be signed by the subject after thorough review of the study is completed with the physician and his/her designee.

#### **4.2 Eligibility Verification/Registration**

Before potential subjects are registered into the study, an eligibility checklist (Appendix A) must be completed to confirm the subject meets the eligibility criteria. The eligibility checklist will be maintained in the study file as source documentation if it has been reviewed, signed, and dated prior to registration by the treating physician.

Subjects will be registered through the sponsor site (UNMC) by contacting the UNMC Project Coordinator. Study personnel from UNMC will contact the UNMC Research Project Coordinator if a subject appears to meet the eligibility criteria. They will email the following information:

- Registration request with Demographics cover sheet (located in the Study site Manual)
- Signed, completed eligibility checklist (Appendix A)
- Copy of the signed and dated consent form

Once the UNMC Research Project Coordinator confirms that the subject meets criteria, and target accrual has not been met, approval for the subject will be given and study subject number assigned. An email confirmation of registration is sent by the UNMC Research Project Coordinator to the site. The project coordinator can assign a subject study number prior to final registration confirmation of a subject.

Each subject consented to the protocol is loaded into the UNMC Clinical Trial Management System (CTMS) within 7 days of consent. CTMS registration includes entering the required demographic information as stated in the SRC policies and procedures.

#### **4.3 Randomization**

The protocol will randomize subjects to two subsequent arms (10 subjects per arm): group 1 will get a CD34+ selected graft + autologous DLI on day+7, while group 2 will get standard G-CSF mobilized graft only.

The process of a 1:1 randomization between the experimental and control arms. During the registration procedures, study personnel are provided the randomization assignment from the the

IIT Office project coordinator. The 1:1 randomization will be conducted using blocked randomization with blocks of size 2 or 4.

#### **4.4 Instructions for Subjects Who Do Not Start Assigned Protocol Treatment**

If a subject does not receive any assigned protocol treatment after consenting, baseline data will be collected and included in the electronic data capture system.

### **Section 5.0 Treatment Plan of Research Design:**

#### **5.1 Outline of research plan**

The protocol will randomize subjects to two subsequent arms (10 subjects per arm): group 1 (experimental) will get a CD34+ selected graft + autologous DLI on day+7, while group 2 (control) will get standard G-CSF mobilized graft only. Nebraska Medicine Biological Production Facility (BPF) personnel will perform processes outlined in Sections 5.1.4 through 5.1.9 below.

##### **5.1.1 Pre-transplant Tetanus Vaccine**

Vaccination can start whenever the subject is in reasonable physical condition to move forward to AHSCT (VRd 3-6 cycles) with a minimum of partial response by IMWG, and at least 2 weeks since the last doses of bortezomib, lenalidomide or dexamethasone. Tetanus (without pertussis) is given pre-transplant as an intramuscular injection. Tetanus vaccination will be documented in the medical record per usual clinical practice. Data needed for the study data set will be recorded from this information.

##### **5.1.2 Immune Correlative Studies**

In all subjects, 70 mls of peripheral blood will be obtained (four tablespoon full) will be collected from all subjects for baseline immune correlative studies. A similar amount of blood will be collected at pre-G-CSF, graft pheresis and on days +15 (+/- 3), +30 (+14), +70 (7-14 days post last dose of tetanus vaccine), +100 (+/-10), and 180 (+/-10) post-transplant to analyze initial post-vaccine immune response. More details in section 5.7.

Test	Time point	Pre vaccine	Pre - PBMC harvest/Pre G-CSF	Graft Pheresis/PBSC graft day	Day + 15 (+/- 3)	Day + 30 (+14)	Day + 70 (+14)	Day + 100 (+/- 10)	Day + 180 (+/- 10)
T-cell Elispot ELISA	X	X			X	X	X	X	
Flow	X	X	X	X	X	X	X	X	
ELISA to Tetanus	X	X			X	X	X	X	

##### **5.1.3 Pre-G-CSF PBMC (DLI) Pheresis**

Seven to 10 days after vaccine, subjects in group 1 will undergo mononuclear leukapheresis to collect and freeze PBMC product for DLI. Subjects will be apheresed for a target blood processed volume of 24-28 liters or as the patient tolerates and per standard UNMC BPF practice. Lymphocyte content of the apheresed product as well as subset analysis will be determined by a cell differential count and flow cytometry.

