**Abstract:**

Because curative therapy for multiple myeloma is not yet available, the treatment goal is to produce lengthy asymptomatic disease remissions. High dose chemotherapy with autologous hematopoietic stem cell transplant (AHSCT) provides optimal remission outcomes, and is the current standard of care for transplant eligible patients. However, some patients experience early relapse. One possible explanation for early relapse is poor immune recovery after high dose chemotherapy given before AHSCT. Harvesting an autologous transplant graft product from circulating blood is facilitated by administration of granulocyte colony stimulating factor (G-CSF) to mobilize large numbers of hematopoietic stem cells into the circulation. The cells are collected from the blood with apheresis and stored until the transplant. Our preliminary studies show that immune suppressor cells are also mobilized and collected in the graft product. Depletion of these suppressor cells in the graft before transplant provided enhanced T-cell reactivity to allogeneic antigens and lymphocyte homeostatic expansion. The hypothesis is that depleting majority of immune suppressive cells from G-PBSC graft in vitro in the setting of AHSCT will tip the balance towards accelerated lymphocyte expansion in-vivo, which will be reflected in high ALC numbers on day 15 ( $>500/\mu\text{l}$ ). The goal is to achieve this depletion via selection and infusion of CD34+ cells, thereby eliminating MDSC's and T-reg's which have an immunosuppressing effect on immune reconstitution. This pilot randomized Phase II trial (10 subjects per arm) will compare immune reconstitution following transplantation of an autologous mobilized graft product to reconstitution following transplantation of a mobilized graft product followed by an autologous lymphocyte infusion collected prior to G-CSF mobilization. All subjects will receive tetanus vaccines pre and post-transplant. The primary end point will be tetanus vaccine immune responses post-transplant.

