**Schema:**

As shown in the schema above:

- 1- Subjects in all groups will receive tetanus vaccine 7-10 days prior to mobilization.
- 2- Subjects in group 1 will have mononuclear cells collected and frozen 7-10 days after tetanus vaccination pre-transplant. These subjects will then receive a CD34+ selected graft on day 0 and autologous donor lymphocyte infusion (DLI) on day +7.
- 3- Subjects in group 2 will receive a standard G-CSF mobilized graft on day 0 without any DLI post-transplant.
- 4- Subjects in all groups will receive G-CSF as subcutaneous injections daily (10 µg/kg) x 5 days starting on day -11 (following the DLI pheresis in the experimental group). Subjects will receive one dose of plerixafor, a stem cell mobilizer, followed by pheresis on the next day to collect G-PBSC graft, with the goal of  $> 6.0 \times 10^6$  CD34+ cells/kg.
- 5- On day of G-PBSC pheresis, the graft in group 2 will be analyzed for CD34, lymphocyte content, and T-reg and MDSCs (cell differential and flow cytometry). Then it will be processed and frozen as per local institutional standards.
- 6- The stem cell product will start to be washed while waiting for the CD34+ content to be known. CD34+ stem cells will then be selected out of the G-PBSC mobilized graft the same day using clinical grade CD34+ magnetic beads and Clinimacs device from Miltenyi as per manufacturer's instructions and as described below. The CD34 content will be analyzed before freezing in liquid nitrogen.
- 7- The subjects in all groups will receive high dose chemotherapy Melphalan at 200 mg/m^2 on day -1.

8- On day 0, subjects in group 1 will receive the thawed CD34+ stem cell graft, while subjects in the group 2 will receive the standard thawed G-PBSC graft. Transplanted CD34+ stem cell dose both groups will be in the range of 2-10 X 10^6/Kg body weight.

9- On day +7 post-transplant, the stored autologous donor lymphocyte product in group 1 will be thawed and infused back to the subjects.

10- **No planned G-CSF post-transplant** (unless medically deemed necessary due to slow engraftment by day 15)

11- Subjects will be followed closely in the hospital until engraftment and resolution of all transplant related toxicities.

12- Subjects will be closely evaluated for any trial related adverse events, specifically: delayed engraftment, auto-immune side effects (autologous graft versus host disease), and infections.

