#### 2.4 Antigen specific immune reconstitution

Riemer et al. evaluated the antigen specific humoral immune response post AHSCT in 38 patients. He found that IgG antibody titers against measles, mumps, rubella, and polio were present in almost all patients pre-transplant and during 12 months post-transplant, indicating persistent humoral immunity. Svane et. al. evaluated the antigen specific cellular immune responses post AHSCT in breast cancer patients. Peripheral blood was collected from five breast cancer patients at serial time points in connection with chemotherapy treatment and in a follow-up period of 1 year. The frequencies of CD8 and CD4 T-cells responsive to cytomegalovirus (CMV), varicella zoster virus (VZV), and tetanus in antigen-activated whole blood were determined by flow cytometric analysis of CD69, (intra-cellular) TNF $\alpha$ , and IFN $\gamma$  expression. Mononuclear cells were labeled with PKH26 dye and the CMV, VZV, and tetanus toxoid-specific proliferation of T-cell subpopulations was analyzed by flow cytometry. In none of the patients did the treatment result in loss of overall T-cell reactivity for any of the antigens. Prior to chemotherapy 5/5 patients possessed TNF expressing T-cells specific for CMV, 4/5 for VZV, and 3/5 for tetanus. One year after stem cell transplantation all patients possessed TNF expressing T-cells specific for CMV, VZV and tetanus. The highest percentages of cytokine responding T-cells were seen after stimulation with CMV antigen. **In general, the lowest antigen specific immune reactivity (close to zero) was measured in G-CSF-mobilized blood at the time of leukapheresis.** Despite a continuously reduced CD4 to CD8 ratio after transplantation, recovery of antigen specific CD4 T-cells usually occurred prior to CD8 recovery and often to a higher level. This study demonstrated that natural as well as vaccine-induced specific immunity established prior to AHSCT can be regained after stem cell transplantation.

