## 2.10 Feasibility of CD34+ selection for clinical applications

The feasibility of CD34+ hematopoietic stem cell selection in AHSCT was demonstrated in the late 90s as a strategy of purging the graft from cancer cells. This approach was tested in a large randomized phase III MM trial and shown to be safe, however there was no improvement in PFS or OS. CD34+ stem selection using the immune-magnetic bead approach is now FDA approved allogeneic stem cell transplant in acute myeloid leukemia. Previously completed phase II trial demonstrated feasibility of engraftment with as low as 2.0 million x 10^6/Kg body weight CD34+ selected stem cell graft for patient with hematologic malignancy.

[figure not shown]
Therefore, combining a pre G-CSF peripheral blood mononuclear cells (PBMC) pheresis product (autologous DLI) with CD34+ selected stem cells may produce a graft with minimum immune suppresser cells, enhanced immune reconstitution and vaccine immune response post AHSCT.

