#### 5.1.5 Stem cell mobilization

Subjects in all groups will receive G-CSF as subcutaneous injections daily (10 µg/kg/day) x 5 days starting on day -11 (after 1st leukapheresis for groups 1). Subjects will receive one dose of plerixafor followed by pheresis on the next day to collect G-PBSC graft. No Cyclophosphamide mobilization is allowed on this protocol. Follow standard of care for stem cell collection.

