## Section 7.0 Study Parameters

Examinations and Assessments	Baseline (Screening)	Pre-Transplant (SCT)				Transplant	Post Transplant Period										Follow up Period
	Pre vaccine	Vaccine (day -19)	Day -12 to -9	Day -11 to -7	Day -6 to -4	AHSCT Hospitalization	Day + 7	Day +15	Day +30	Day +60	Day +70	Day +100 (mo. 3)	Day +130 (mo. 4)	Day +150 (mo. 5)	Day +180 (mo. 6)	Day +365 (1 yr)	Survival status (2 years)
Tetanus Vaccine		X						X		X							
Group 1  / Pre G-CSF PBMC pheresis			X														
Group 1 – Post-AHSCT PBMC infusion							X										
G-CSF (both groups)				X													
Pre Stem Cell harvest / Graft Pheresis (both groups) 					X												
Immune correlative study blood draw		X	X 		X			X	X		X	X		X			

 Pre-PBMC harvest in group 1 7-10 day post vaccine only

Clinical Assessment is billed as physical exam with performance score. Data will be collected for MM disease specifics. Height and weight are also collected only at screening.

 Disease response to be done at discretion of physician in keeping with standard of care.

 Transplant day is day 0.

 Female of child-bearing potential must have two negative urine pregnancy test results within at time of eligibility testing and prior to GCS-F pre-transplant as a way of ensuring safe transplant planning.

Organ function measured by standard clinical care labs collected from CBC, complete metabolic panel to assess the kidney, liver function.

 Subjects will receive one dose of plerixafor, a stem cell mobilizer, followed by pheresis on the next day to collect G-PBSC graft

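### With the calendar's day -19 vaccine, the lymphocyte harvest window (days -12 to -9), the day -11 G-CSF start and the stated harvest-before-G-CSF order cannot all be met

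*Combined protocol and SAP*

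**What the plan says.** **Harvest.** Section 5.1.3, titled as a pre-G-CSF pheresis, states: "Seven to 10 days after vaccine, subjects in group 1 will undergo mononuclear leukapheresis to collect and freeze PBMC product for DLI". Schema item 2 gives the same interval. Neither gives a calendar day.

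**Vaccine.** The Section 7.0 calendar has a column headed "Vaccine (day -19"). Schema item 1 uses a different anchor: "Subjects in all groups will receive tetanus vaccine 7-10 days prior to mobilization".

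**Calendar columns.** Section 7.0 places the group 1 harvest on days -12 to -9, G-CSF on days -11 to -7 and graft pheresis on days -6 to -4.

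**G-CSF.** Schema item 4 gives five daily doses "starting on day -11 (following the DLI pheresis in the experimental group"). Section 5.1.5 repeats this: "starting on day -11 (after 1 st leukapheresis for groups 1"). Each sentence therefore fixes both a day and an order.

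**What the product is meant to be.** The Abstract describes an "autologous lymphocyte infusion collected prior to G-CSF mobilization". Section 2.10 gives the rationale as "combining a pre G-CSF peripheral blood mononuclear cells (PBMC) pheresis product (autologous DLI) with CD34+ selected stem cells".

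**Paired blood sample.** Section 7.2 places a correlative draw 7-10 days after the vaccine, before both the harvest and G-CSF. For group 1 the calendar puts it in the same days -12 to -9 column.

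**The concern.** Collection before G-CSF is what defines the lymphocyte product, and that product is one of the two components that separate the experimental arm from the control arm. If the dates do not deliver the stated order, whoever schedules the subject must decide which instruction to break, and different subjects may be handled differently.

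Either choice has a cost. Following the order shifts the G-CSF days for some group 1 subjects away from the stated start, while controls have no harvest to wait for. Following the day numbers yields a product that does not meet its own definition, and a blood sample labelled pre-G-CSF that is not. With 10 subjects in the arm, each affected subject is 1/10 = 10% of it, and the plan has no stated way to identify such a subject at analysis.

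**Working it through.** This is calendar arithmetic. The power statement in Section 10.5 does not bear on it.

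**Inputs.** Vaccine day -19 (Section 7.0 column header only). Harvest 7 to 10 days after vaccine (Schema item 2, Section 5.1.3). First G-CSF dose on day -11, five daily doses, after the harvest (Schema item 4, Section 5.1.5).

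**Step 1: reproduce the calendar's columns.**
- Harvest: -19 + 7 = -12 and -19 + 10 = -9, so days -12 to -9. This matches the column.
- G-CSF: -11 + 4 = -7, so days -11 to -7. This matches the column, which holds exactly five doses with no slack.

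**Step 2: test each harvest day h against both rules.** G-CSF dosing days before the harvest day = max(0, h - (-11)).

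| Days after vaccine | Harvest day | Earlier G-CSF dosing days | Day -11 start and harvest first? |
|---|---|---|---|
| 7 | -12 | 0 | Yes |
| 8 | -11 | 0 | Only if harvest precedes that day's dose |
| 9 | -10 | -10 + 11 = 1 | No |
| 10 | -9 | -9 + 11 = 2 | No |

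**Step 3: what follows if the order governs.** Assume G-CSF starts on the harvest day, or on day -11 if the harvest was earlier, and that the graft is first collected the day after the fifth dose.
- Harvest on day -10: G-CSF on days -10 to -6, first collection on day -5.
- Harvest on day -9: G-CSF on days -9 to -5, first collection on day -4.

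Both leave the G-CSF column. First collections still fall within days -6 to -4. However, Section 5.1.6 sends subjects who mobilize 6-10 million CD34/kg to a second collection day. After a day -9 harvest that would be day -4 + 1 = -3, outside the graft column.

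If G-CSF starts the day after harvest instead, a day -9 harvest gives G-CSF on days -8 to -4 and a first collection on day -3.

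**Step 4: does the Schema's own anchor guarantee the order?** Take mobilization in Schema item 1 as the first G-CSF dose on day -11. The vaccine then falls between -11 - 10 = -21 and -11 - 7 = -18.

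| Vaccine day | Harvest window (+7 to +10) | Days past -11 |
|---|---|---|
| -21 | -14 to -11 | 0 |
| -20 | -13 to -10 | 1 |
| -19 | -12 to -9 | 2 |
| -18 | -11 to -8 | 3 |

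Only a day -21 vaccine keeps every harvest day at or before day -11. Harvest and G-CSF are both placed 7-10 days after the same vaccine, so the intervals alone do not fix which comes first.

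**The case against.** The strongest reply is that the protocol never permits a harvest after G-CSF. The order is written into both G-CSF sentences, into the title of Section 5.1.3, into the name of the calendar row and into the Abstract. A site that follows it would delay G-CSF, and with a same-day start the first graft collections still fit the graft column. A reader might infer from the overlapping columns that the plan allows G-CSF-exposed lymphocyte products. The documents do not support that: exposure would arise only if someone scheduled by day number and ignored the stated order. This part of the reply stands. It does not rescue the schedule, because the day -11 start and the days -11 to -7 column then fail instead.

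A second reply is that the days -12 to -9 range depends on day -19, which appears only in the calendar. Section 5.1.3 gives an interval alone, and Section 5.1.1 ties vaccination to fitness and time since induction drugs. That is correct. It narrows the exact overlap to the calendar's case, but Step 4 shows that the Schema's intervals do not secure the order either.

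Third, a reader might take Section 2.4 as proof that an early-exposed product would respond poorly, since "the lowest antigen specific immune reactivity (close to zero) was measured in G-CSF-mobilized blood". That finding concerns mobilized blood at the time of leukapheresis in five breast cancer patients. It says nothing about blood after one or two doses.

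Finally, Section 11.1 already requires dated dosing notes and Section 9.3.1 provides for review of protocol violations. These would help to detect a breach. They do not settle which instruction applies, and dates alone cannot order two events on day -11.

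**Conclusion.** The schedule contradicts itself. Given the calendar's day -19 vaccine, two of the four listed harvest days (-10 and -9) cannot meet both the day -11 G-CSF start and the stated order, and a third (-11) can do so only in one sequence within the day. The same applies to the group 1 blood sample that shares the column.

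This counts calendar days. It does not estimate how many subjects would be affected, and it does not show that any product would be exposed to G-CSF. The documents give no figure for the effect of one or two doses on the tetanus response, so no dilution of the treatment contrast can be claimed or sized. The Step 3 dates rest on the assumed G-CSF start rule and next-day collection. The graft column may instead have been meant for collection over several days.

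The intent is clear and consistently stated; the dates do not carry it out. Because the step defines the experimental product and the correction is cheap, it should be corrected.

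**What to change.** Reconcile the Schema (items 1, 2 and 4), Sections 5.1.3 and 5.1.5 and the Section 7.0 calendar, so that every permitted harvest day and pre-G-CSF sample day is consistent with the protocol's own stated order. Which days to use is for the sponsor and investigators; this review proposes none.

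Record the date and time of the lymphocyte harvest, of the paired blood draw where it is taken separately, and of the first G-CSF dose. Flag any product or sample collected after G-CSF began, report the number, and state in Section 10 how flagged subjects and samples will be handled.

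The cost is wording in four places, two date/time fields (a third if the draw is timed separately) and one sentence in the analysis section. Sample size and tests are unchanged.
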